9.0 Patient Withdrawal and Trial Discontinuation

9.1 Criteria for Subject Off-Therapy

Subjects may be withdrawn from the study treatment for the following reasons:

- Subject completes all protocol defined therapy- 27 cycles
- Relapsed neoplastic disease
- Subject or guardian withdraws consent to continue study drug
- Subject develops an intercurrent illness that precludes further participation, or requires a prohibited concomitant treatment
- The Investigator withdraws the subject in the subject's best interests
- Subject is lost to follow-up (defined as the inability to contact the subject on 3 separate occasions over a period of 2 weeks)
- Administrative reasons (e.g., the subject is transferred to hospice care)
- An adverse event, which in the opinion of the Investigator, precludes further trial participation or fulfills the protocol requirements for withdrawal (e.g., the development of dose limiting toxicity despite a reduction in protocol therapy for a previous episode of dose limiting toxicity)
- Death

9.2 Criteria for Subject Off-Study

Subjects may be withdrawn from the study completely which includes survival follow-up for the following reasons:

- Subject or guardian withdraws consent to continue in the trial
- Subject is lost to follow-up (defined as the inability to contact the subject on 3 separate occasions over a period of 2 weeks)
- Subject completes all protocol defined therapy including all follow-up time points.
- Death

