1. Additional imaging or assessments may be done if clinically indicated. Type of imaging, type of assessment and timing should be recorded as well as reason for imaging and/or assessment.
2. Survival will be monitored on an ongoing basis during the study, then every 6 months from the time the subject is off-treatment for a period of 2 years, then yearly for up to five years off therapy.

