7.8 Protocol Treatment Completion

Subjects who receive 27 total 28-day treatment cycles will be considered as having completed protocol (total of 756 days).

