7.10 Survival Follow-up

Subjects will be followed for long term survival by contact with parent or treating institution to confirm survival at the following time points (time from last dose of study drug):

- | | |
|-------------|-------------------------------------|
| - 6 months | -2 years |
| - 1 year | -Yearly after (up to 5 years total) |
| - 18 months | |

Follow up will continue for five (5) years off-therapy or until subject death or subject is lost to follow up (per definition in section 9.0). The follow-up results including follow-up status, remission status, and date of death will be recorded on the appropriate page of the CRF, as well as in the subject's source documentation.

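### Sections 9.2 and 7.10 end survival follow-up on a two-week failed-contact rule, although off-treatment contacts are 6 to 12 months apart and no return to follow-up is described

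*Combined protocol and SAP*

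**What the plan says.** Section 9.1 lists reasons for coming off study drug and section 9.2 lists reasons for leaving the study altogether. Loss to follow-up is in both lists with the same definition: "Subject is lost to follow-up (defined as the inability to contact the subject on 3 separate occasions over a period of 2 weeks". The lead-in to the 9.2 list reads "Subjects may be withdrawn from the study completely which includes survival follow-up for the following reasons".

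Section 7.10 is firmer. It states "Follow up will continue for five (5) years off-therapy or until subject death or subject is lost to follow up", and refers to section 9.0 for the meaning of loss.

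Section 7.7 (Other Schedules) sets the timing of survival contact after treatment: "every 6 months from the time the subject is off-treatment for a period of 2 years, then yearly for up to five years". Section 7.10 gives the same schedule as time points after the last dose: 6, 12 and 18 months, 2 years, then yearly up to 5 years. It describes the means as "contact with parent or treating institution to confirm survival", and asks sites to record remission status as well as vital status.

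Sections 10.4 and 10.5 run EFS and OS from the first dose, and a patient without the event is counted to last contact. Section 7.8 sets treatment length: "Subjects who receive 27 total 28-day treatment cycles will be considered as having completed protocol (total of 756 days".

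**The concern.** One definition serves two purposes. During treatment a subject is due in clinic every 28 days, and two weeks of silence is informative about whether treatment is continuing. In long-term follow-up nothing is expected from the family for 6 or 12 months at a time. Three unanswered attempts within two weeks may then mean only that the family is away or has moved. Under 7.10 those attempts can close the patient's follow-up for good.

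The stake is the quality of censoring, OS first. If families become hard to reach because the child has relapsed, changed hospital or died, censoring at last contact is related to outcome and the survival curve reads too high. If they drift away because the child is well, the bias runs the other way. The trial has a single arm, so no concurrent control group shares the distortion.

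**Working it through.** **1. The provisions side by side.**

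| Provision | Trigger | Consequence | Force |
|---|---|---|---|
| 9.1 | 3 failed contacts with the subject over 2 weeks | off study drug | permissive |
| 9.2 | identical | off study, including survival follow-up | permissive |
| 7.10 | loss as defined in 9.0, so the same | follow-up ends | stated as what will happen |

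None of the three requires an enquiry to the parent or institution before loss is declared, and none describes resuming follow-up or updating status if the subject is found.

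**2. The window against the contact interval.** Two weeks is 14 days.

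- 6-month interval: 14 / (365.25 / 2) = 14 / 182.6 = 0.077, about 8%.
- Yearly interval: 14 / 365.25 = 0.038, about 4%.

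**3. What an early closure gives up.** The 7.10 schedule has seven time points: 6, 12 and 18 months, then 2, 3, 4 and 5 years. A patient closed at the first one loses the other six, which is 5 − 0.5 = 4.5 years of planned follow-up.

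**4. Where the two-year EFS point falls.** The plan's treatment length reproduces: 27 × 28 = 756 days. Two years is 2 × 365.25 = 730.5 days. Twenty-six cycles end at day 26 × 28 = 728, so the two-year point lies in cycle 27, and treatment ends 756 − 730.5 = 25.5 days after it. Through this period section 7 has a Day 1 visit each cycle, with scans at the end of cycles 3, 6, 9, 13, 20 and 27. For a patient who completes 27 cycles without interruption, the 6- to 12-month interval does not apply before two years.

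**5. Which outcomes are exposed.**

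- OS: exposed, because it depends on off-treatment contact for up to five years.
- Two-year EFS: exposed for patients who stop DFMO early without an event, who move to the sparse schedule before two years, and for patients lost on treatment under 9.1 and then closed under 9.2.
- EFS beyond two years: exposed, since it rests on the remission status collected at the 7.10 contacts.

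**6. What cannot be computed.** The documents give neither a loss rate nor the share of lost patients who could be found again. The relevant quantity is the extra loss that this rule adds to whatever loss would occur anyway, and nothing in the documents supplies it.

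**The case against.** Several points on the other side have force.

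- Section 9.2 is permissive, so a site may keep trying. That is true of 9.2, but 7.10 ties the end of follow-up to the same definition without that latitude.
- The treating institution is already a routine contact source in 7.10, so the plan does not ignore it. This stands. In a paediatric trial, contacting the subject may also reasonably be read as contacting the family. The gap is narrower: the definition names only the subject and does not require the other sources to be tried before closure.
- Relapse and transfer to hospice are off-therapy reasons in 9.1 and are absent from the 9.2 list. Neither ends survival follow-up by itself, and a recorded relapse is already an EFS event. This weakens the outcome-related route to loss, but leaves relapses and deaths that occur after contact lapses.

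Three stronger readings are tempting and are not supported. A reader might infer that the rule undermines the primary two-year EFS result generally, but the 28-day visits cover that point for completers. A reader might infer that lost patients drop out of the analysis, but sections 10.4 and 10.5 keep them in to last contact. A reader might count every lost patient as a failure in the Stratum 1 binomial test and quote a loss of power. The plan states a count cut-off only for Stratum 2 (7 of 33), nowhere says that lost patients are failures, and allows Stratum 1 enrolment of up to 140 to secure 127 evaluable. Such a figure would also charge all loss to this one rule. How the binomial test treats patients with unknown two-year status is a separate gap, which changing 9.2 would not close.

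**Conclusion.** The point holds in a limited form. The off-study definition does not suit a follow-up phase with contacts 6 to 12 months apart. Together, 9.2 and 7.10 can close follow-up early with no stated way back. The main consequence is early and possibly informative censoring of OS, with a partial effect on EFS in the three situations listed above.

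No size can be given. The direction of any bias is also not fixed by the documents, because it depends on why contact fails. The conclusion rests on sites following 7.10 as written. Where sites already keep trying through the parent or institution, the practical effect may be small. This is a cheap improvement and not a threat to the design.

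**What to change.** Keep the two-week definition in section 9.1 only. In sections 9.2 and 7.10, replace it with wording to this effect:

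- A failed contact at a scheduled survival time point is recorded as a missed time point, not as loss.
- Before loss is declared, the site must have enquired of the parent or the treating institution.
- Contact attempts continue at later scheduled time points.
- If the subject is found, follow-up resumes and disease and vital status are updated, unless consent to follow-up has been withdrawn.

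The cross-reference in 7.10 should then point to 9.2 and no longer to section 9.0 as a whole. How many missed time points count as final loss is the sponsor's choice.

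The cost is amendment wording, a few more contact attempts per unreachable patient, and a later declaration of loss.

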9.3 Trial Discontinuation

The lead site may discontinue the trial as a whole or at an individual investigational site at any time. Reasons for early trial discontinuation may include, but are not limited to, unacceptable toxicity of study drug, a request to discontinue the trial from a regulatory authority, protocol violations at an investigational site, violations of good clinical practice at an investigational site, or poor enrollment. The lead site will promptly inform all Investigators in the event of premature study discontinuation and provide all Investigators with instructions regarding the disposition of subjects still on study. Should the study be terminated prematurely, all unused study drug, case report forms and any other study material will be returned to the lead site.

10.0 DATA ANALYSIS

10.1 Data Quality Assurance

Electronic case report forms (CRF) will be checked for correctness against source document data by the monitor. If any entries into the CRF are incorrect, incomplete or illegible, the monitor will ask the Investigator or the study site staff to make appropriate corrections.

10.2 Statistical Analysis

This is an open label, single agent, multicenter, study for patients with neuroblastoma that are in remission.

The following data sets will be used in this study:

- All enrolled and eligible subjects (ITT) population: All eligible subjects who have a signed informed consent form.
- All treated and eligible subjects (Safety evaluable) population: All subjects who received at least one dose of study drug
- All eligible subjects treated to first evaluable time point with evaluation completed (generally 3 cycles) (as Treatment Efficacy) population, unless subjects have reached the study endpoint of progression of disease at an earlier time point.

Efficacy analyses will be performed on the Treatment evaluable population. Safety analysis will be performed on the Safety and Efficacy evaluable population.

10.3 All baseline patient characteristics will be summarized in a tabular format. Safety data will be described for all subjects receiving at least one dose of DFMO. Safety data will include values for hematology, serum chemistry, vital signs, and adverse events. The proportion of subjects experiencing adverse events, serious adverse events, dose limiting toxicities and treatment delays will be summarized. Enrollment to study will not pause at interim analysis time points.

Sample Size and Analysis:

Stratum 1:

A 70% 2-year EFS rate was selected as the Phase I baseline rate. The baseline 70% EFS rate at 2-years was based upon published data by Yu et al. (82). It is hypothesized that DFMO will increase the 2-year EFS rate to 80% which represents an approximately 10% increase in the duration of the EFS rate at 2-years. Assuming a directional 5% one population binomial test, a sample size of $n = 127$ patients will be required to achieve an 80% power to detect this 2-year difference in EFS (70% vs 80%).

The comparison of the biomarker prevalence rates assumes that the Stratum 1 cohort will experience a relapse rate of 30% and thus a 70% non-relapse rate at up to two years of follow-up. It is also assumed that the corresponding prevalence of an elevated biomarker will be 60% for the relapse group and 30% in the non-relapse group, respectively. This hypothesized prevalence difference will be detectable with 85% power with an overall sample size of N=127 patients (38 relapse and 89 non-relapse) using a Fisher's Exact Test and a non-directional Type I Error level of 5%.

The sequential biomarker data over the course of treatment for each patient will be classified as elevated or not based upon the following *a priori* study criteria and blinded to patient progression status. Elevation of the biomarker is defined as diacetylspermine levels > 500nmol/gm creatinine on 2 consecutive urine levels. The biomarker prevalence rates for the patients who progress (estimated to be n= 38) and those who do not progress (estimated n=89) over the two years of the trial treatment will be compared using a Fisher's exact test of the equality of the two EFS prevalence rates implemented with a 5% two-tailed Type I error level. A 95% exact confidence interval for the absolute difference in prevalence rates along with a 95% exact confidence interval for the odds ratio for the resulting prevalence rates will be obtained to complement the formal hypothesis testing. Since OS will also be a secondary outcome for comparing the utility of the biomarker prevalence, time-to-event analyses will also be implemented using the Kaplan-Meier approach initially using the *a priori* biomarker definition. These initial time-to-event analyses will then be supplemented with a Cox proportional hazard modeling effort using the quantitative biomarker assessment to allow for an exploratory analysis of other cut-point definitions that can be used to contrast with that of the original *a priori* definition. Potential confounding clinical measures that are identified for the recurrent and non-recurrent patients will be incorporated in a limited fashion using Cox proportional hazard models that also include the biomarker effect. This exploration of confounders will need to be limited due to the anticipated small sample sizes. Data from this stratum will guide the statistical design for a Phase II study in this patient population.

Stratum 2:

Based upon tabled median EFS times all patients presented by Santana et al. (Cancer, June 15, 2008) for first and second recurrence times, a median first recurrence time of 8.7 months is equivalent to a 14.8% EFS at two years, and the median time to a subsequent second recurrence of 3.8 months is equivalent to an EFS rate of 1.3% at two years assuming an exponential time-to-event model. Assuming that two thirds of the relapse patient population will have had only a single relapse and that the other third of the patients will have had two or more relapses, then a weighted average of these two EFS rates (14.8% and 1.3%) equals 10.3%. A 10% historical EFS rate for two years was assumed for simplicity. Examination of an increase in EFS will require a sample size of n = 33 subjects in Stratum 2 to test whether treatment with DFMO can prolong the overall estimated EFS at two years to 30% from the 10% two years estimate for the above historical data in this patient population. The sample size is based upon a one sample binomial test of proportions with a power 80% and a 5% two -tailed Type I error level.

An observation of 7 or more patients with at least a two year EFS rate out of the $n = 33$ patients will result in the rejection of the null hypothesis of a 10% EFS in favor of the alternative of a 30% two year EFS rate. An exact binomial 95% confidence interval for the two year estimated EFS will complement the prior formal two-stage hypothesis test. Since the actual EFS time-to-event data is derived from the times to recurrence, a Kaplan-Meier analysis of the time-to-event data analysis will be conducted, and the median time to recurrence and a 95% confidence for this value will be obtained to supplement this EFS point estimate. Since this group of Stratum 2 patients will consist of patients with prior single and multiple recurrence histories, EFS and time to event data will be examined by prior recurrence histories. In particular, the impact of prior recurrence history on the time to recurrence will be explored using Kaplan-Meier analysis and Cox proportional hazard models. The response to DFMO therapy and subsequent recurrences will also be explored in combination with prior recurrence histories using Cox models.

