	
Subjects will be evaluated in 2 strata:
 
 • Stratum 1: Subjects that are in remission at the end of upfront therapy defined as chemotherapy (5-7 cycles), surgery as indicated, consolidation therapy as indicated, radiation therapy as indicated, anti-GD2 antibody therapy with retinoic acid up to 6 cycles. • Stratum 2: Subjects that are in remission after any previous relapse or refractory therapy 
Stratum 1- A total of 127-140 subjects in Stratum 1 will be enrolled to ensure that there will be 127 evaluable subjects.
 
Stratum 2- A total of 38 subjects in Stratum 2 will be enrolled to ensure that there will be 33 evaluable subjects.

ELIGIBILITY
	
Inclusion Criteria
 
 1. Age: 0-21 years at the time of diagnosis. 2. Diagnosis: histological verification at either the time of original diagnosis or a previous relapse of high risk neuroblastoma. 3. Disease Status: Neuroblastoma that is in Remission 4. Greater than 30 days from completion of cytotoxic and antibody therapy and less than 120 days from previous therapy. 5. A negative serum or urine pregnancy test is required for female subjects of child bearing potential (onset of menses or ≥ 13 years of age). 6. Both male and female post-pubertal study subjects need to agree to use one of the more effective birth control methods during treatment and for six months after treatment is stopped. These methods include total abstinence (no sex), oral contraceptives (“the pill”), an intrauterine device (IUD), levonorgestrol implants (Norplant), or medroxyprogesterone acetate injections (Depo-provera shots). If one of these cannot be used, contraceptive foam with a condom is recommended. 7. ANC > 500/μl and platelet count >50,000/μl 8. Organ Function Requirements

Subjects must have adequate liver function as defined by
 AST and ALT <10x upper limit of normal
 Serum bilirubin must be ≤ 2.0 mg/dl
 Serum creatinine based on age/gender as follows:

Age	Maximum Serum Creatinine (mg/dL)	
	Male	Female
1 month to < 6 months	0.4	0.4
6 months to < 1 year	0.5	0.5
1 to < 2 years	0.6	0.6
2 to < 6 year	0.8	0.8
6 to < 10 years	1	1
10 to < 13 years	1.2	1.2
13 to < 16 years	1.5	1.4
≥ 16 years	1.7	1.4

9. Informed Consent: All subjects and/or legal guardians must sign informed written consent. Assent, when appropriate, will be obtained according to institutional guidelines

Exclusion Criteria

1. Lansky score < 60%

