CRITERIA FOR EVALUATION	
Preventative Activity Measures: Primary objectives
 
 • Event Free Survival (EFS), defined as period from the first day of administration of study drug to the first occurrence of relapse, progressive disease, secondary cancer, or death or, if none of these events occurred, until the last contact with the subject. 
Safety Measures and Preventative Activity Measures: Secondary objectives
 
 • Correlation of urinary polyamine levels with progression of disease in neuroblastoma. • Overall Survival (OS) will be defined as the first day of administration of study drug until death or will be censored at the last contact with the subject if death did not occur during the study. • Safety analysis will be conducted on all subjects who have received at least one dose of study drug, and will include the frequency of all adverse events and laboratory abnormalities as well as frequency of dose interruptions, dose reductions and treatment discontinuation.

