6.5 Concomitant Medications and Treatments

All intercurrent medical conditions will be treated at the discretion of the Investigator according to acceptable community standards of medical care. All concomitant medications and treatments will be documented on the appropriate case report form.

The following medications are not permitted during the trial:

- Any cytotoxic chemotherapy
- Any other investigational treatment
- Any other systemic anti-neoplastic therapy including, but not limited to, immunotherapy, hormonal therapy, targeted therapies, anti-angiogenic therapies, or monoclonal antibody therapy
- Any radiotherapy, including systemically administered radioisotopes, unless administered with palliative intent

Erythropoietin, blood products, anti-emetics, steroids, and transfusions may be administered at the discretion of the Investigator based on established criteria

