10.4 Event Free Survival

The event free survival (EFS) is defined as the period from the first day of administration of study drug until the first occurrence of relapse, progressive disease, secondary cancer, or death or, if none of these events occurred, until the last contact with the subject.

Progression is defined as the appearance of any new lesions >10mm on CT/MRI, any new lesions on MIBG or new disease present in the bone marrow.

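### The efficacy set keeps early failures only if they are progressions, so an early death without documented progression is an EFS event that drops out of the primary test

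*Combined protocol and SAP*

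**What the plan says.** Section 10.2 defines three sets: eligible subjects with signed consent (called ITT), subjects with at least one dose (safety), and eligible subjects treated to the first evaluable time point with that evaluation completed, generally 3 cycles. The third set has one exception: "unless subjects have reached the study endpoint of progression of disease at an earlier time point". The section then states: "Efficacy analyses will be performed on the Treatment evaluable population". The set has a slightly different name in its definition, but no other set fits. No efficacy analysis is assigned to the ITT or all-treated set.

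Section 10.4 runs EFS from the first day of study drug "until the first occurrence of relapse, progressive disease, secondary cancer, or death". The Synopsis (Criteria for Evaluation) lists the same four events. Section 10.4 also defines progression narrowly: "Progression is defined as the appearance of any new lesions >10mm on CT/MRI, any new lesions on MIBG", or new disease in the marrow.

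On numbers, the Synopsis (Study Design) says for Stratum 1: "A total of 127-140 subjects in Stratum 1 will be enrolled to ensure that there will be 127 evaluable subjects". For Stratum 2: "A total of 38 subjects in Stratum 2 will be enrolled to ensure that there will be 33 evaluable subjects".

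**The concern.** The endpoint has four kinds of event, and the rule that keeps early failures in the analysis names one. Two kinds of EFS failure fall through:

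- A death before the first evaluation with no documented progression. If progression was found on an earlier unscheduled scan, the subject stays in.
- A secondary cancer in a subject who then does not complete the first evaluation. This could happen because treatment barred by section 6.5 is needed (its list begins with "Any cytotoxic chemotherapy"), which is a reason to stop study drug under section 9.1. A subject with a secondary cancer who does complete the evaluation stays in.

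Every such subject is a certain failure, so leaving one out can only raise the observed EFS rate. Each stratum is tested against a fixed historical rate (70% or 10%), and no concurrent arm undergoes the same selection. An early death on study drug is exactly the kind of outcome that the primary endpoint is meant to count.

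Early toxicity stops and withdrawals are also excluded. They are a different matter, because they raise EFS only if their risk of failure is above average.

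**Working it through.** **Who is in the set.** Take a subject who dies in cycle 2 with no scan or marrow evidence of progression.

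| Question | Source | Answer |
|---|---|---|
| EFS event? | 10.4, Synopsis | Yes, death |
| Completed the first evaluation? | 10.2 | No |
| Covered by the exception? | 10.2, with progression as in 10.4 | No |
| In another set used for efficacy? | 10.2 | No |

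**The plan's own figure.** Inputs from section 10.3 (Stratum 1): n = 127, one-sided 5% binomial test, 70% versus 80%, power 80%. The plan states no cut-off, so it is derived here from the exact binomial distribution:

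- P(X ≥ 97 | 127, 0.70) = 0.0682, above 5%
- P(X ≥ 98 | 127, 0.70) = 0.0453, so the cut-off is 98
- power P(X ≥ 98 | 127, 0.80) = 0.820, in line with the stated 80%

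**Effect of k excluded failures.** Suppose that the true EFS among all treated subjects is 70% and that 127 + k are treated to obtain 127 evaluable. The k are all failures, so the EFS rate in the evaluable set is 0.70 × (127 + k)/127.

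| k | EFS in evaluable set | P(X ≥ 98 of 127) |
|---|---|---|
| 0 | 0.7000 | 0.045 |
| 1 | 0.7055 | 0.059 |
| 2 | 0.7110 | 0.077 |

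A result exactly at the boundary shows the same thing. 98/127 has p = 0.045; putting one failure back gives 98/128 with p = 0.061, which no longer rejects.

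**How plausible is k = 1 or 2?** The documents give no early-event rate. Assume a constant hazard, which the plan does not state for Stratum 1: h = −ln(0.70)/730.5 = 0.000488 per day. The end of cycle 3 is day 3 × 28 = 84, and the ±14-day scan window in section 7.5 gives days 70 to 98. The proportion with any EFS event by day d is f = 1 − exp(−dh). One excluded failure is a share 1/(128f) of the expected early events, and two are 2/(129f).

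| Day | f | Early events in 128 | Share for k = 1 | Share for k = 2 |
|---|---|---|---|---|
| 70 | 3.4% | 4.3 | 23% | 46% |
| 84 | 4.0% | 5.1 | 19% | 39% |
| 98 | 4.7% | 6.0 | 17% | 33% |

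The share is that of early events which are not progression and which miss the evaluation. If it is s, the evaluable EFS is 0.70/(1 − s·f), and the type I error is:

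| Assumed s | Day 70 | Day 84 | Day 98 |
|---|---|---|---|
| 5% | 0.048 | 0.049 | 0.049 |
| 10% | 0.051 | 0.052 | 0.053 |
| 20% | 0.057 | 0.060 | 0.063 |

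**Stratum 2.** The same gap applies. No error rate is derived, because the stated rule of 7 of 33 has an upper-tail probability of 0.042 at 10%, while the plan describes the test as 5% two-tailed. The nominal level is therefore itself unclear.

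**The case against.** - **Loose wording.** The exception speaks of a study endpoint, and the study endpoint is EFS, not progression. Section 10.3 calls the 38 expected Stratum 1 failures patients who progress, and for Stratum 2 it derives EFS times from times to recurrence. The authors may have meant any EFS event. That is quite possible, but section 10.2 does not say so and section 10.4 defines the term narrowly, so an analyst following the text would drop these subjects.
- **Size.** Subjects enter in documented remission, and early death without relapse may be rare. At a 5% share the type I error stays under 5%; 0.059 and 0.077 require one or two such failures. This stands, and it is why the effect is called probably small.
- **Timing.** The day 70 to 98 range is not a firm bound. Section 10.2 says generally 3 cycles, and section 7.5 lets first-remission patients substitute previously scheduled evaluations with approval. This stands too: the shares are illustrative.
- **Replacement.** No replacement rule is written. It is inferred from enrolling to an evaluable count, and the margin allows at most 140 − 127 = 13 and 38 − 33 = 5 extra subjects.
- **Deaths are still reported.** They appear in the safety data and reach the DSMB. That puts them on record but does not put them in the EFS test.
- **The remedy goes further than the gap.** Changing one phrase closes the gap described. Moving to all dosed subjects is the fuller option and partly a design choice.

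**Conclusion.** The concern holds on the text as written: the only set used for efficacy omits some events that the primary endpoint counts. For the failures described, the direction is certain and favours DFMO. The size is not known. One excluded failure in Stratum 1 moves the type I error from 0.045 to 0.059, and two move it to 0.077. For assumed shares of 5% to 20% of early events, it lies between 0.048 and 0.063. These figures rest on the derived cut-off of 98/127, a true all-treated EFS of 70% and, for the shares, a constant hazard with a first evaluation between days 70 and 98. The gap should be fixed: the trial is open label with a single arm, a boundary result can turn on one subject, and the correction is cheap.

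**What to change.** **Minimum.** In section 10.2, replace the reference to progression in the exception with *any EFS event as defined in section 10.4*. This is one phrase and costs nothing.

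**Preferred.** Make the primary EFS and OS set all eligible subjects with at least one dose of DFMO, count every section 10.4 event from the first dose, and keep the evaluable set as supportive. Retain the exact binomial test of 2-year EFS as the single primary test, with its cut-off recomputed for the number analysed. For Stratum 1 (one-sided 5%, null 70%):

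| n | Cut-off | Type I error | Power at 80% |
|---|---|---|---|
| 127 | 98 | 0.045 | 0.820 |
| 128 | 99 | 0.040 | 0.807 |
| 130 | 100 | 0.049 | 0.838 |
| 135 | 104 | 0.043 | 0.834 |
| 140 | 108 | 0.037 | 0.830 |

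Report the Kaplan-Meier 2-year EFS with section 10.4 censoring beside it, not as a second primary test.

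State how an unknown 2-year status enters the binomial test. Counting it as not event-free is one option, but it costs power: with 140 dosed, cut-off 108 and true EFS 80%, P(X ≥ 108 | 140 − u, 0.80) is 0.830, 0.786, 0.736 and 0.551 for u = 0, 1, 2 and 5 unknown. Section 7.10 limits the loss, since it records remission status to 2 years after the last dose and beyond. However, it schedules no scans, and under section 9.2 withdrawal of consent or loss to follow-up ends follow-up.

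Section 6.3 discontinues subjects with unresolved toxicity from the study, while the off-study list in section 9.2 does not include toxicity. The two must be reconciled so that it is clear whether these subjects' status is collected.

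The full change is SAP wording and a recomputed cut-off, with no new procedures. The EFS estimate may come out slightly less favourable.
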